1. INTRODUCTION

AF is the most common disturbance of heart rhythm. With a UK prevalence of 7.2% in patients aged 65 and over and 10.3% in patients aged 75 and over ⁽¹⁾ AF has considerable impact on quality of life and NHS resources ^(2,3). Treatment of AF and its consequences (anti-arrhythmic and anti-coagulant drugs, hospital monitoring & stroke treatment) is expensive for the NHS. Implementation of the recent NICE guidelines (June 2006) ⁽²⁾ on management of AF is estimated to cost £21.86m per year. ⁽³⁾ The NHS devotes 5% of its budget to strokes and 15% of these are associated with AF.⁽¹⁾ Routine anticoagulation is used to reduce the risk of stroke, however this incurs an increased risk of bleeding and the burden of monitoring treatment falls on general practice, anticoagulant clinics and haematology laboratories.

AF ablation devices are a new and costly technology being marketed to treat this condition. The use of this technology is increasing in NHS practice despite the lack of good research evidence to support adoption.

The study will test the hypothesis that treating AF by incorporating a modified maze procedure (using an ablation device) into elective cardiac surgery will promote a return to SR and improve quality of life as well as being cost-effective from an NHS perspective.

Elective cardiac surgical patients with pre-existing AF will be randomly allocated to receive, or not receive, a device-based maze procedure as an adjunct to their operation (' adjunct maze '). As this is a pragmatic, ' real-life ', trial the ablation devices will be those in routine use in the participating centres. The trial is not designed or powered to distinguish between different types of device.

AF occurs in around 30% of patients after cardiac surgery. It has a multifactorial aetiology, arises out of micro-re-entry circuits and is usually self-terminating. The management of this complication has been extensively studied ⁽⁴⁾ and is outside the scope of this trial.

1.1 Existing research

The current basis for treatment and management of AF is dealt with in a UK NICE Guideline (2006) ⁽²⁾ a Cochrane review ⁽⁵⁾ and European Guidelines ⁽⁴⁾. International recommendations on surgical and catheter ablation of AF were published in 2007 jointly by the Heart Rhythm Society, European Heart Rhythm Association and European Cardiac Arrhythmia Society in their Expert Consensus statement ⁽⁶⁾.

A number of studies (cited in ref.6) suggest that AF not only marks out a prospective cardiac surgery patient as high risk but that AF is also an independent risk factor for operative morbidity and mortality. This leads to the (unproven) hypothesis that efforts to eliminate pre-existing AF during cardiac surgery may improve survival and reduce adverse cardiac events after surgery.

The maze procedure can be performed in two ways:

1. The traditional cut-and-sew technique, known as the Cox-maze with its many modifications, is reliable in restoring sinus rhythm in the majority of patients (references cited in 6). Despite being available since 1987, this procedure has signally failed to achieve widespread use. The main reason for this is that it is technically demanding and adds substantially to the operative burden of a heart operation. It is currently in very limited use by a few surgeons in a few centres and tends to be reserved for otherwise fit patients with

severely symptomatic AF who are prepared to take the risk of a major intervention to relieve their symptoms.

2. The ablation device maze procedure uses an energy source (heat, cold, radiofrequency or microwave) to replicate the lesion set of the Cox-maze. As a rule, the procedure is safe, well tolerated and adds little to the length and burden of the operation.

There has been no direct comparison between traditional Cox-maze and ablation maze, presumably due to the problems of incorporating such technically demanding surgery into an adequately powered randomised controlled design. However a propensity analysis which matched patients who underwent ablation maze with those having Cox-maze showed no differences in freedom from AF at 3, 6 and 12 months afterwards ⁽⁷⁾.

Common sense suggests that treating AF at the time of cardiac surgery is advantageous to the patient. However the only evidence supporting this comes from 5 small randomised controlled trials of ablation devices as adjuncts to surgery ⁽⁸⁻¹²⁾. These trials found that SR was restored in 44 – 94% of treated patients compared to 5 - 33% of controls. The trials were small and follow-up was short. Success was mostly defined on the basis of single ECG recordings. No trial looked at patient-centred outcomes or cost effectiveness. Despite this lack of robust evidence, an increasing number of patients with AF having open heart surgery are now being offered concomitant ablation maze procedures (' adjunct maze ') (cited in ref. 6).

We therefore have a situation where there is no rigorous evidence that attempting to restore SR by treating AF with an ablation device during cardiac surgery is of benefit to the patient. Nevertheless these devices are being incorporated into routine practice nationally and internationally. The recent Expert Consensus Statement on Catheter and Surgical Ablation of Atrial Fibrillation ⁽⁶⁾ developed by Heart Rhythm Society in partnership with European Heart Rhythm Association and European Cardiac Arrhythmia Society has launched a call for high quality prospective multi-centre trials to adopt consistent definitions of procedural success in long term assessments of the safety and efficacy of ablation maze.

The proposed trial will respond to this call and inform patients, clinicians and the NHS about the routine adoption of this technology.

2. STUDY OBJECTIVES

The primary objective of assessing patient benefit will be achieved by comparing the two groups for the rate of return to stable SR at 12 months as well as quality-adjusted survival over 2 years. 4-day ECG monitors will be used to assess the predominant rhythm (SR or AF) and the AF load ie the percentage of time that the patient is in AF if the predominant rhythm is SR.

The secondary objective of assessing cost-effectiveness for the NHS will be achieved by collecting resource use data and costs incurred by both groups and comparing their costs per quality-adjusted life year (QALY). Further longer term economic modelling will also be undertaken.

Other secondary objectives will be to determine whether the adjunct maze procedure

- improves the rate of return to stable SR at 24 months after surgery,
- decreases thromboembolic neurological complications (eg stroke),
- enables anticoagulant treatment to be withdrawn safely,
- enables safe reduction or withdrawal of antiarrhythmic medication.

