3.3 Study population

Eligible patients will be consecutive elective cardiac surgical patients undergoing major cardiac surgery (such as coronary, valve or combined operations) with a history of paroxysmal, persistent or chronic AF beginning more than 3 months before the date of the operation.

- Paroxysmal AF is defined as recurrent AF (> 2 episodes) that terminates spontaneously within 4 days (Expert Consensus Statement on Catheter and Surgical Ablation of Atrial Fibrillation). ⁽⁶⁾
- Persistent AF is defined as AF which continues beyond 4 days.
- Chronic or longstanding AF is persistent AF beyond 1 year.

Inclusion criteria:

- age over 18
- elective cardiac surgery planned (coronary surgery, valve surgery, combined coronary and valve surgery, any other cardiac surgery requiring cardiopulmonary bypass.)
- history of documented atrial fibrillation (chronic, persistent or paroxysmal) beginning more than 3 months before entry into the study
- written informed consent to participation

Exclusion criteria:

- previous cardiac operations
- emergency or salvage cardiac operations
- surgery without cardiopulmonary bypass
- unlikely to be available for follow-up over a two-year period
- deemed not competent to provide consent

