5. OUTCOME MEASURES

5.1 Primary outcomes:

i) Return to SR at 12 months

The number of patients in SR at 12 months after surgery will be determined by 4-day ECG monitors that will be provided for patients to wear continuously for 4 days at 12 months after their operation.

ii) Clinical effectiveness - quality-adjusted survival over 2 years

Clinical effectiveness will be measured by QALYs, which will be calculated by combining length of survival and the EQ-5D (administered at randomisation, on discharge and at 6 weeks and 6, 12 and 24 months after the procedure).

5.2. Secondary outcomes:

- (i) Clinical endpoints of SR at 24 months after surgery, overall survival and stroke-free survival, incidence of anticoagulant-related haemorrhage.
- (ii) Health-related quality of life measured by the EuroQoL, SF-36 & NYHA (for breathlessness)
- (iii) Resource use and cost-effectiveness of the adjunct maze procedure.
- (iv) Anticoagulant and antiarrhythmic drug usage.

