6.4 Analysis of ECG recordings

All 4 day continuous ECG recordings will be analysed centrally at Papworth Hospital. Participating centres will be requested to forward the SD cards from the ECG recorders to Papworth Hospital. Analysis of this data using the proprietary automated software package, together with manual checking of the recording in its entirety, will be done. Total time spent in sinus rhythm and in AF (AF burden) during the 4 day recording will be calculated, with only those episodes of AF lasting greater than 60 seconds duration included in the analysis. Episodes of atrial flutter will be noted and included in the AF burden.

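### The rhythm co-primary aims at stable sinus rhythm, but the only classifier the protocol prints is predominant rhythm, which patients with considerable AF time could meet

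*Protocol*

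**What the plan says.** Protocol section 2 describes the first part of the primary objective as "comparing the two groups for the rate of return to stable SR at 12 months". It then says how rhythm is to be read: "4-day ECG monitors will be used to assess the predominant rhythm (SR or AF"). It describes AF load as "the percentage of time that the patient is in AF if the predominant rhythm is SR".

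Section 5.1 defines the outcome without a threshold: "The number of patients in SR at 12 months after surgery will be determined by 4-day ECG monitors". Section 7.1 compares the proportions in SR by likelihood ratio test, again with no rule for who is in SR.

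Section 6.4 sets out the reading of the recordings: "Total time spent in sinus rhythm and in AF (AF burden) during the 4 day recording will be calculated". A filter on episode length applies to that calculation: "with only those episodes of AF lasting greater than 60 seconds duration included in the analysis". The section adds: "Episodes of atrial flutter will be noted and included in the AF burden".

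Section 3.3 admits paroxysmal as well as persistent and chronic AF: "Paroxysmal AF is defined as recurrent AF (> 2 episodes) that terminates spontaneously within 4 days".

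Section 3.5.1 sizes this endpoint on 45% v 30% in SR, with 176 per group for 80% power at two-sided 5%. The rates draw on references 8–12. Section 1.1 says that success in those trials was mostly judged on single ECGs.

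**The concern.** A binary co-primary endpoint needs a rule that turns a 4-day recording into success or failure. The protocol uses three phrases for success (stable SR, predominant rhythm, in SR), and only predominant rhythm says anything about classification. It is also the most lenient of the three. By attaching an AF load to patients whose predominant rhythm is SR, section 2 accepts that a patient classed as SR may have AF time, and it sets no limit.

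Three things follow:

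- The endpoint could count as stable SR a recording that few readers would call stable.
- A paroxysmal patient who was mostly in SR before surgery could be recorded as having returned to SR when nothing had changed, in either arm.
- AF load restricted to patients classed as SR is measured in a subset chosen by a post-randomisation outcome. A comparison of the arms on it is no longer protected by randomisation.

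If the rule stays open, it could also be settled after recordings have been read.

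**Working it through.** **1. The protocol's own figure.** Inputs from section 3.5.1: p1 = 0.45, p2 = 0.30, d = 0.15, mean 0.375, two-sided 5%, power 80%.

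n = [1.960·√(2·0.375·0.625) + 0.842·√(0.45·0.55 + 0.30·0.70)]² / 0.15² = 162.3, so 163 per group.

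With continuity correction: n/4·[1 + √(1 + 4/(n·d))]² = 175.4, so **176 per group**, an exact match. At 176 per group, power is 80% continuity-corrected and 83% uncorrected. The result depends only on the two rates, so reproducing it does not show which definition of SR they refer to.

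**2. How far apart the possible rules are.** The recording lasts 4 × 24 = 96 hours.

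- Predominant rhythm, read as more than half the time: just under 48 hours of AF is still a success.
- No episode over 60 seconds: one 61-second episode is a failure. That is 61/(96 × 3,600) = 0.018% of the recording.

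The permitted AF time could therefore lie anywhere from about 0% to 50%.

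**3. What a stricter rule might cost.** The documents give no SR rate under a stricter rule, so this is an assumption. Take 45% v 30% as predominant-rhythm rates, and let a share f of SR patients in each arm have an episode over 60 seconds and become failures. The rates become 0.45(1−f) and 0.30(1−f). Continuity-corrected power uses the effective size N(1 − 1/(N·d))² with N = 176.

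| f | Rates | N per group for 80% power (corrected) | Corrected power at 176 |
|---|---|---|---|
| 0 | 45.0% v 30.0% | 176 | 80% |
| 0.1 | 40.5% v 27.0% | 206 | 73% |
| 0.2 | 36.0% v 24.0% | 245 | 65% |
| 0.3 | 31.5% v 21.0% | 294 | 56% |
| 0.4 | 27.0% v 18.0% | 359 | 47% |

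If f differs between arms, the result can move either way. With f = 0.1 treated and 0.3 control, the rates are 40.5% v 21.0% and uncorrected power is 98%. With the shares reversed they are 31.5% v 27.0%, and it is 15%.

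**4. Whether paroxysmal patients must dilute the effect under predominant rhythm.** The protocol gives neither their share nor their SR rates. Assume that non-paroxysmal patients follow 45% v 30% and mix in a paroxysmal share s. For s = 20% and paroxysmal rates of 95% v 90%, the overall rates are 0.8·0.45 + 0.2·0.95 = 55% and 0.8·0.30 + 0.2·0.90 = 42%. Uncorrected power at 176 per group, against 83%:

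| Paroxysmal SR rates | s = 20% | s = 30% |
|---|---|---|
| 95% v 90% | 69% | 62% |
| 95% v 80% | 81% | 81% |
| 90% v 80% | 75% | 72% |
| 80% v 60% | 86% | 88% |

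The range is 62% to 88%, so the direction depends on the assumed inputs.

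**The case against.** The strongest reply is that a numerical cut-off is ordinary analysis-plan detail, that section 2 never expressly makes predominant rhythm the success rule, and that no 50% limit is printed. The last two points are correct, and the 48-hour figure is an inference from a word. But the protocol does more than leave a detail open: its objectives section prints a classifier, and that classifier does not match the stated aim.

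A reader might infer that section 6.4 contradicts section 2 by making any AF episode over 60 seconds a failure. It does not. The 60 seconds decides which episodes enter the AF-time calculation. That filter is compatible with predominant rhythm and with AF load, and section 7.1 analyses patients in SR, not episodes.

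A reader might also infer a definite loss of power from paroxysmal patients. The second table above does not support one. Nor would a stricter rule fully remove the problem, because a paroxysmal patient may have no episode in a given four days. Randomisation balances these patients in expectation, and section 7.1.1 already plans a paroxysmal v non-paroxysmal subgroup analysis.

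On AF load, the objection partly stands. Section 6.4 derives AF time from all recordings, and section 5 does not list AF load as an outcome. The restriction in section 2 is therefore poor wording with an easy remedy, and no listed comparison is shown to be biased. The documents also give no basis for a special rule on paced or junctional rhythm.

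**Conclusion.** The point holds as a mismatch between objective and classifier for a co-primary endpoint. Section 2 aims at stable SR and prints predominant rhythm; sections 5.1 and 7.1 do not resolve it. On the ordinary meaning of the word, patients with considerable AF time, and paroxysmal patients already mostly in SR at baseline, could count as having returned to SR. AF load limited to patients classed as SR conditions on a post-randomisation outcome.

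The size of the misclassification cannot be computed from the documents. The span of possible rules, about 0% to 50% AF time, rests on reading predominant as more than half. The documents do not support a conflict with the 60-second filter or a fixed power loss.

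The planning rates are a related loose end. They come from trials that mostly used single ECGs, and the titles of references 8–11 name chronic, permanent or continuous AF. The protocol does not say which definition 45% v 30% is meant to describe under 4-day monitoring.

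**What to change.** - Remove predominant rhythm as the classifier in section 2, and state one rule for SR at 12 months, in the same words, in sections 2, 5.1 and 7.1. It should match stable SR: for example, no AF or atrial flutter episode over 60 seconds on the 4-day recording, using the episodes that section 6.4 already identifies. Keep predominant rhythm at most as a sensitivity analysis.
- Report AF burden for every patient with a recording, as section 6.4 already calculates it, and delete the restriction in section 2.
- In section 3.5.1, say which definition the 45% v 30% rates refer to, and revisit the power if it is not the one adopted.

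The first two changes need only wording, because the recordings and episode data are already planned. The real cost is lower SR rates in both arms and possibly lower power, on the scale of the first table if the planning rates describe predominant rhythm. If they already describe a rule as strict as the one adopted, that loss does not arise. The gain is an endpoint that is fixed in advance and measures what the objective names; higher power is not promised.

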3. INVESTIGATIONAL PLAN

3.1 Design:

The proposed study will be a multi-centre, prospective, double blind, randomised controlled trial to compare clinical, patient-based and cost outcomes for patients with pre-existing AF who undergo routine cardiac surgery either with or without an adjunct device-based ablation procedure (' adjunct maze ').

The trial will be double blind to the extent that neither the patient nor the cardiologist who analyses the 4-day ECG, nor the quality of life assessor will be aware which group the patient has been allocated to. Where possible the standards of design and reporting of this trial will adhere to the guidelines of the CONSORT statement ⁽¹³⁾ and incorporate recommendations of the Expert Consensus Statement on Catheter and Surgical Ablation of Atrial Fibrillation ⁽⁶⁾.

3.2. Setting and Investigators

Eight acute NHS cardiac surgical centres (Papworth, Brompton, Brighton, Coventry, Leicester, Manchester, Sheffield, St Thomas's) will participate with Papworth Hospital as the lead centre. Each centre already has one or more surgeons experienced in the use of ablation devices and further training will be incorporated into the study. They are all members of the UK AF Study Group with interest in surgical treatment of AF and one member ([name]) has published on this topic. ⁽¹⁰⁾

3.3 Study population

Eligible patients will be consecutive elective cardiac surgical patients undergoing major cardiac surgery (such as coronary, valve or combined operations) with a history of paroxysmal, persistent or chronic AF beginning more than 3 months before the date of the operation.

- Paroxysmal AF is defined as recurrent AF (> 2 episodes) that terminates spontaneously within 4 days (Expert Consensus Statement on Catheter and Surgical Ablation of Atrial Fibrillation). ⁽⁶⁾
- Persistent AF is defined as AF which continues beyond 4 days.
- Chronic or longstanding AF is persistent AF beyond 1 year.

Inclusion criteria:

- age over 18
- elective cardiac surgery planned (coronary surgery, valve surgery, combined coronary and valve surgery, any other cardiac surgery requiring cardiopulmonary bypass.)
- history of documented atrial fibrillation (chronic, persistent or paroxysmal) beginning more than 3 months before entry into the study
- written informed consent to participation

Exclusion criteria:

- previous cardiac operations
- emergency or salvage cardiac operations
- surgery without cardiopulmonary bypass
- unlikely to be available for follow-up over a two-year period
- deemed not competent to provide consent

3.4 Devices

This is a pragmatic clinical trial to assess outcomes in a 'real world' context. Furthermore, there is no evidence whatsoever for the superiority of one device or one energy source over another. We will therefore include any AF ablation device that is routinely used within the NHS by the investigators. This will allow surgeons to use the devices with which they are most familiar and comfortable. However, the trial will record which device and which

energy source were used for individual patients and some subgroup analysis will be undertaken.

3.5 Recruitment

3.5.1 Sample size

The primary outcome includes a purely clinical end point as well as an outcome of importance to patients.

It consists of: 1) return to sinus rhythm (SR) at 12 months and 2) clinical effectiveness measured as quality-adjusted survival over 2 years. Sample size calculations are based on both these primary endpoints.

1) Return to SR at 12 months.

Published RCTs of ablation as an addition to cardiac surgery have reported rates of return to SR at 12 months ⁽⁸⁻¹²⁾ ranging from 44% to 87% in the trial arms and 5% to 33% in the control arms. If we take a conservative estimate of the difference between the groups (45% vs. 30%) then we would have 80% power to detect this difference with a sample size of 176 in each group, total 352 (2-sided significance 5%). With recruitment of 400 patients this would allow for deaths or loss to follow up at 12 months of approximately 15%.

2) Clinical effectiveness measured as quality-adjusted survival over 2 years.

The emphasis in cost-effectiveness studies is on estimation rather than hypothesis testing so that formal sample size calculations are less important. However, we provide a power calculation based on the effectiveness measure QALY. We could find no studies reporting comparative QALYs in similar patients undergoing ablation and cardiac surgery. From previous studies of patients undergoing angiography for suspected ischaemic heart disease ⁽¹⁶⁾ and patients with refractory angina ⁽¹⁷⁾ the standard deviation of QALYs over 12 and 18 months is at most 0.3. Over follow up of 2 years the minimum clinically important improvement is considered to be one extra month of quality-adjusted life, or 0.083 QALYs. With a sample of 200 patients per group, total 400, we would have approximately 80% power to detect a difference of 0.083 QALYs, (2-sided significance 5%). If the accepted threshold for cost effectiveness were in the range £20-30,000 per QALY and we could demonstrate a significant increase in QALYs of 0.0833, then the procedure would be cost-effective for an incremental cost of at most £2,500.

3.5.2 Feasibility of proposed recruitment:

Our proposed sample size is 400 recruited over 18 months from a minimum of 6 centres. A survey of the centres interested in participating shows that they conduct an average of approximately 800 cardiac surgical procedures per year per centre. More than 10% of these patients will be in AF giving an average eligible population of at least 80 patients per year per centre. We propose to recruit 400 patients over 18 months, so the rate of recruitment will average 43 patients per year per centre. This means that we only need to recruit half the eligible patients to achieve our proposed recruitment rate. Previous experience shows that patients are generally very willing to consent to this adjunct surgical procedure as it presents very little additional risk and could possibly relieve them of their debilitating AF symptoms.

The proposed recruitment rate translates to 3 to 4 procedures per month which is considered to be well within the capability of the participating centres (see Appendix 2 Recruitment Schedule).

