4. INTERVENTION

4.1 Randomisation

Eligible patients who fulfil the inclusion criteria, have provided full written consent and have had sufficient time for discussion and consideration, will be randomised (in a 1:1 ratio) to one of two groups. They will receive either their routine cardiac surgery with no additional procedure or their routine cardiac surgery with an adjunct maze procedure.

Patient allocations will be computer generated by the trial statistician and will be in random permuted blocks of variable lengths, stratified by surgeon and by planned cardiac procedure (CABG, aortic valve, mitral valve, combined procedure).

On the day of surgery, when the patient is in the anaesthetic room, the local centre will register the participating patient with Papworth Hospital R&D Unit by telephone or fax.

Patient details, surgeon and planned cardiac procedure will be recorded by R&D unit staff not otherwise directly involved with the trial. Once registration is complete the group allocation will be released to the surgical team who will also be responsible for completing the surgical data forms. The group allocation will not be made available to any other staff who are directly involved with the trial.

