Appendix 1. Recruitment and randomisation (at Papworth)

Appendix 2. 07/01/34 The clinical and cost effectiveness of adding an ablation devicebased maze procedure as an adjunct to elective cardiac surgery for patients with pre-existing atrial fibrillation. The Amaze trial (n = 400)

	Baseline	Surgery	6 week visit	6 month	12 months	24 months	Total - new	Total	Total
Month			(routine)	VISIT	VISIT		patients	rollow-ups	episodes
1		ART UP:	Appoint staff,	iocai proje	ect teams, I	SC, DMEC	. Oversee re	gulatory ap	provais all
2	Agree proto	cole Sur	nical & resear	ch staff tr	oining Esta	blich report	ing & monito	ring strated	w Initiato
3	sites		gical & researc	SIT Stall lie	anning. Lota	blishi tepon		ning strateg	ly. Initiate
4	15						15		15
5	16	15					16		16
6	16	16	13				16	13	29
7	20	16	15				20	15	35
8	25	20	15				25	15	40
9	25	25	19				25	19	44
10	25	25	23				25	23	48
11	25	25	24	13			25	37	62
12	18	25	24	15			18	39	57
13	20	18	23	15			20	38	58
14	24	20	19	19	-		24	38	62
15	24	24	18	23	-		24	41	65
16	25	24	24	24			25	48	73
17	24	25	23	24	12		24	59	83
18	25	24	24	23	14		25	61	86
19	24	25	23	19	14		24	56	80
20	24	24	24	18	18		24	60	84
21	25	24	22	24	22		25	68	93
22		25	23	23	23		0	69	69
23			24	24	22		0	70	70
24				23	22		0	45	45
25				24	18		0	42	42
26				22	17		0	39	39
27				23	23		0	46	46
28				24	22			46	46
29					22	12		34	34
30					22	14		36	36
31					23	14		37	37
32					21	18		39	39
33					22	22		44	44
34					23	23		46	46
35						22		22	22
36						22		22	22
37						18		18	18
38						17		17	17
39						23		23	23
40	Primary &	secondar	/ outcome and	lucie & ro	norting	22		22	22
41					porting	22		22	22
42			1117			22		22	22
43						23		23	23
44						21		21	21
45						22		22	22
46						23		23	23
47									
48		Lon	g term analysi	s and rep	orting (not f	unded by H	ITA)		
49									
Totals	400	400	380	380	360	360	400	1480	1880
NOTE:									

352 patients are required for analysis of return to sinus rhythm at 12 months after surgery. 15% drop out is anticipated - this consists of 5% post surgical mortality and an additional 10% failure to provide primary outcome data. To accommodate this attrition we will recruit 400 patients.

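### Recruiting 400 does not cover 15% attrition for 352 evaluable patients: 15% loss leaves 340, and 352 of 400 allows only 12%

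*Protocol*

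**What the plan says.** Protocol section 3.5.1, item 1, takes sinus rhythm rates at 12 months of 45% and 30% and claims "80% power to detect this difference with a sample size of 176 in each group, total 352 (2-sided significance 5" per cent). It continues: "With recruitment of 400 patients this would allow for deaths or loss to follow up at 12 months of approximately 15" per cent.

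The note under the recruitment table in Appendix 2 makes the same link in three steps:

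- the requirement: "352 patients are required for analysis of return to sinus rhythm at 12 months after surgery";
- the expected loss: "15% drop out is anticipated - this consists of 5% post surgical mortality and an additional 10% failure to provide primary outcome data";
- the conclusion: "To accommodate this attrition we will recruit 400 patients".

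The table above that note ends in the row "Totals 400 400 380 380 360 360 400 1480 1880". In column order this is 400 at baseline and at surgery, 380 at 6 weeks and 6 months, and 360 at 12 and 24 months, followed by the workload totals.

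Section 7.1 limits the 12-month rhythm analysis to patients who have a 4-day ECG result at that time, and compares groups by likelihood ratio tests. Section 4.1 fixes allocation at 1:1.

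**The concern.** The protocol states a required number of evaluable patients, an expected loss and a recruitment target, and says that the target covers the loss. These three figures should satisfy one equation, and they do not. The rhythm analysis uses only patients with a 12-month ECG, so every death or missing recording comes straight off the analysed number. If attrition runs exactly as the protocol expects, the trial falls below the number that the protocol says it requires. What is at stake is whether the stated 80% power and the stated attrition allowance describe the same trial.

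**Working it through.** **Inputs.** Rates 0.45 and 0.30, two-sided 5%, 80% power, 176 per group and 352 in total, 400 recruited, about 15% loss (section 3.5.1). Loss of 15%, made up of 5% mortality and 10% missing primary outcome data (Appendix 2 note). Equal allocation (section 4.1).

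**1. Reproduce 176 per group.** The mean rate is 0.375.

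n = [1.960 × √(2 × 0.375 × 0.625) + 0.842 × √(0.45 × 0.55 + 0.30 × 0.70)]² / 0.15² = 162.3, so 163 per group (326 in total).

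With the usual continuity correction:

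n′ = (n/4) × [1 + √(1 + 4/(n × 0.15))]² = 175.4, so 176 per group (352 in total).

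The stated figure therefore reproduces exactly with the correction. The protocol does not name its formula; the correction is inferred from this match.

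**2. Check the attrition step.**

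| Question | Calculation | Result |
|---|---|---|
| Evaluable after 15% loss | 400 × 0.85 | 340, which is 12 short of 352 |
| Evaluable if 5% and then 10% are lost in sequence | 400 × 0.95 × 0.90 | 342, which is 10 short |
| Loss that leaves 352 | 1 − 352/400 | 12.0% |
| Recruits needed for 352 after 15% loss | 352/0.85 = 414.1 | 415 (416 for equal groups) |

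Multiplying instead of dividing gives 352 × 1.15 = 404.8, which is near 400. That may be how the figure arose, but the protocol does not say.

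**3. Power at the number actually retained.** With n per group and c = 1/n (corrected) or c = 0 (uncorrected):

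power = Φ{[0.15 − c − 1.960 × √(2 × 0.375 × 0.625/n)] / √[(0.45 × 0.55 + 0.30 × 0.70)/n]}

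| Evaluable per group (total) | Corrected | Fisher exact | Uncorrected |
|---|---|---|---|
| 176 (352) | 80.1% | 80.6% | 83.1% |
| 170 (340) | 78.6% | 78.8% | 81.8% |

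On the corrected basis the shortfall costs 80.1 − 78.6 = 1.5 percentage points.

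**4. The same step on the uncorrected basis.** 326/0.85 = 383.5, so 384 recruits would cover 15% loss. With 400 recruits the tolerable loss is 1 − 326/400 = 18.5%.

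**5. The Appendix 2 table.** The monthly entries add up to the printed totals: 400 recruited, 380 at 6 weeks, 380 at 6 months and 360 at 12 months. So 360 is the authors' own figure and implies 1 − 360/400 = 10% fewer visits than recruits.

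**The case against.** **The wording is approximate and the effect is slight.** Section 3.5.1 says only approximately 15%, and 12% might pass as a loose rounding. That defence fails for the Appendix 2 note, which gives 15% without a qualifier, builds it from 5% and 10%, and says that 400 accommodates it. The point about size does stand: power moves by 1.5 points on the corrected basis and stays above 80% on the uncorrected one.

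**The continuity correction is not a fault.** A reader might infer that sizing with a correction and then planning a likelihood ratio test, which has none, is an error. It is not. It is a conservative choice that asks for more patients than the test needs. It matters here only because it explains where 176 comes from and offers one way to make the statement true.

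**The 360 is a visit count.** A reader might infer that 360 visits at 12 months contradict the 15% in the note. The documents do not support that. The table is a workload schedule of visits, follow-ups and episodes, whereas the note counts patients who provide primary outcome data. A patient can attend and still yield no usable ECG: 360 attending less 20 without a recording would leave 340. The protocol does not say that this is the intended reading, so a line of explanation is worth having. The identical 24-month total is a simplification in the schedule and does not bear on the 12-month calculation.

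**No retention target is set for the committees.** A reader might also infer that the oversight committees would monitor retention against a wrong figure. Sections 8.3 and 8.4 refer to milestones and data review but give no retention threshold, so this does not follow.

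**Conclusion.** The statement that 400 recruits cover 15% attrition for 352 evaluable patients is wrong as written, in section 3.5.1 and in the Appendix 2 note. At 15% loss 340 remain. The allowance that fits 352 of 400 is 12%, and 15% would need 415 recruits.

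The consequence is small: 78.6% power at 340 on the basis that reproduces 176, against the stated 80%, or 81.8% without the correction. A reader might infer that the trial is underpowered for sinus rhythm or must recruit 415. Neither follows, because on an uncorrected calculation 400 recruits cover 15% loss with room to spare.

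These figures assume the protocol's 45% v 30%, equal loss in the two groups, and normal-approximation power, with the exact test as a check on the corrected figures. The uncorrected figure stands in for the planned likelihood ratio test as a large-sample approximation.

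**What to change.** Keep 400 and restate the calculation in section 3.5.1 and in the Appendix 2 note, using the same one of these two forms in both places:

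- **Retain 352.** State that 352 evaluable of 400 recruited allows 12% loss, and that at the anticipated 15% loss (340 evaluable) power is about 79% on the basis used for 176 per group. Name the continuity correction.
- **Rebase the requirement.** State that, without a continuity correction and so in line with the planned likelihood ratio test, 163 per group (326) suffice, and that 15% loss from 400 leaves 340 evaluable and about 82% power.

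The second form lets the protocol keep both its 15% expectation and its 80% target. In either case, add a line under the Appendix 2 table saying that the 360 visits at 12 and 24 months are a workload count, and how they relate to the 15% in the note. The totals themselves need not change.

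The cost is a few sentences of wording, with no extra patients and no change to the analysis.
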